## 2.2 Safety

All operative site events as well as all serious adverse events (SAEs), excluding elective procedures, will be collected and reviewed against published data. It is expected that the AE rates reported for the Triathlon TS Total Knee System will be comparable to those reported in

### CONFIDENTIAL

the literature for similar revision TKR systems. Details regarding AE definitions, recording and reporting are in Section 8 of this protocol, Adverse Events.

# 3 Clinical Study Plan

## 3.1 Study Design

A prospective, post-market, multi-center design will be employed. Radiographs will be assessed by an independent reviewer.

## 3.2 Number of Centers

Under Version 1.0 of the protocol, cases were enrolled at 12 centers in the United States. These centers will continue to enroll under Version 2.0. The enrollment goal ranges from 15 to 26 revision TKR cases implanted with the Triathlon TS Total Knee System per center. The enrollment goal range is dependent upon the number of participating centers. Although a range is presented, there is no maximum limit to the number of cases that a center may enroll. In the event that a center far exceeds the enrollment goal, Stryker may ask the center to cease enrollment so as not to skew the data. All participating centers will comply with the federal regulations regarding patient informed consent and IRB approval. Non-compliance of a study center may result in termination of the center's participation in the study.

## 3.3 Number of Subjects

Cases will be enrolled in this study until 181 receive the Triathlon TS Total Knee System as required under this protocol. All cases will receive, at a minimum:

- Triathlon TS Femoral Component in a cemented application
- Triathlon TS Plus Tibial Insert or the Triathlon Posteriorly Stabilized (PS) Tibial Insert
- Triathlon TS Universal Tibial Baseplate in a cemented application.

The subject's patellar component may or may not be revised, based upon surgeon discretion. If revised, a Triathlon Patellar Component must be used, and in a cemented application. Additionally, a variety of device accessories may be used. All components are described in detail in Section 6 of this protocol, Device Description.

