## 1.1 Background

As the population ages, so does the incidence of arthritis and subsequent primary TKR. Frequency of revision for failed TKR increases as well, aimed at alleviating pain and improving function following time-dependent primary implant failure or complications such as infection and fracture. The primary goals of revision TKR are to alleviate pain and provide the patient with stable, well-functioning TKR through optimal implant fixation and restoration of knee biomechanics. Appropriate TKR biomechanics are established through adequate flexionextension gap balancing, proper mechanical and rotational alignment, proper patellofemoral mechanics and restoration of the JL.

Revision TKR outcomes typically decline with each successive revision. However, patient expectations of postoperative function, pain relief and adequate QOL may not be adjusted for the expected decline in functional results observed in revision TKR. Some long-term data exists to describe the effectiveness of revision TKR. Sheng et al. performed a meta-analysis of publications on patient outcomes following revision TKR. Thirty-three studies with a total number of 1356 patients were included in this analysis, which reported increased function and motion compared to preoperative scores. The main indication for revision reported is aseptic loosening (55%). Other reasons include polyethylene wear (11%), instability (10%), infection (7%), progression of disease (4%), osteolysis (4%), bone fracture (4%), component failure (3%), stiffness (1%) and pain of unknown origin (1%). Instability can be caused by malposition of the JL, imbalance in flexion and extension gaps or incompetence of the posterior cruciate ligament.

There is little existing data reporting outcomes for a single type of revision TKR prosthesis, such as the Triathlon TS Total Knee System. To date, differences between various revision TKR implant systems are not reported in the scientific literature. Long-term outcomes data among a new generation of revision TKR prostheses is needed.

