### CONFIDENTIAL

Page 8

In addition to improving patient outcomes, one of the challenges in revision TKR is restoration of the JL. Improper positioning of the JL has been shown to lead not only to instability but also to an increased incidence of anterior knee pain and decreased flexion. Malposition may also lead to patellar infera and posterior soft tissue impingement by the femoral component. Mason et al., in a study of six cadaver knees, investigated four anatomic landmarks for locating the JL during revision knee surgery – the medial femoral epicondyle (ME), the fibular head (FH), the tibial tubercle (TT), and the inferior pole of the patella (IPP). In this study, the distance between the ME and the JL showed very small patient-to-patient variability. As a result, it was concluded that the ME is a reliable and reproducible landmark for JL measurements.

Additionally, Mahoney and Kinsey retrospectively reviewed JL restoration and clinical outcomes in 22 consecutive femur revision cases. The authors used specialized instruments and were able to restore JL to within 2 mm of anatomic position in 12 of the 22 knees. Flexion and extension gap balancing and ME referencing were reliable methods of measuring and achieving proper position of the JL.

As a secondary objective, this outcomes study of the Triathlon TS Total Knee System will also examine the effect of JL restoration on a subset of revision TKR cases with a non-replaced contralateral knee at the time of study surgery. The effect will be evaluated by comparing between cases with JL restoration > 5 mm and cases with JL restoration  $\leq$  5 mm. As little as 5 mm of displacement from the JL can cause laxity in midflexion or tightness, even in a gap-balanced knee.

For all cases, at the time of study surgery, surgeons will intraoperatively measure, in millimeters, the distance between the ME and the JL in full extension and in 90° of flexion. This measurement will be taken before removal of the previous implants as well as after implantation of the final Triathlon® TS Total Knee System.

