#### CONFIDENTIAL

The protocol for measuring JL is referenced in Appendix A. Stability, anterior knee pain and the functional component of the KSS will be evaluated with respect to JL.

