### CONFIDENTIAL

### 2.1.2 Secondary

The secondary objectives of this study will be to evaluate the effect of JL restoration on revision TKR with specific reference to effect on postoperative stability, anterior knee pain and functional performance at 2 and 5 years postoperatively. It is expected that the Triathlon® TS group with JL elevation > 5 mm is non-inferior to the Triathlon TS group with JL elevation  $\leq$  5 mm.

All outcomes other than the change in KSS, already analyzed as the primary objective, will be analyzed from preoperative to 1, 2 and 5 years postoperatively.

Additionally, the long-term performance of the Triathlon TS Total Knee System for revision TKR will be evaluated with regard to radiographic stability, revision rate and complications when reviewed against published data.

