#### CONFIDENTIAL

correspond to the surgical procedure. To assess efficiency, measures of surgical time will be collected to support future improvements.

JL measurements will also be taken intraoperatively according to Appendix A. Investigators will measure, in millimeters, the distance between the ME and the JL. This measurement will be taken in extension and at 90° of flexion, both before and after implantation of the Triathlon TS Total Knee System.

Intraoperative gap measurements will also be obtained by using lamina spreaders to measure the tibio-femoral distance of the medial and lateral compartments in full extension and at 90° of flexion immediately upon removal of the primary implant and adequate debridement of fibrous tissue down to viable bone. Once the lamina spreaders have been applied within each compartment, a ruler should be utilized against the bone to record the distance between the tibia and femur, in millimeters, if the distance cannot be read directly from the instrument.

If available for intraoperative gap measurements, investigators should utilize a femoral tibial tensor spreader which additionally allows applied force to be read so that consistency is maintained in both extension and flexion. This type of instrument may allow for proper tensing of the medial and lateral ligaments and femoral component rotation, to achieve flexion-extension gap balance.

There are numerous measurements required intraoperatively. Appendix A should be referenced for a full summary on required intraoperative measurements. The majority of intraoperative data required is not standard. Appendix A should be referenced in detail so that all source documentation is reflective of non-standard data points collected. All surgical details needed for data collection can be found in Appendix F, on the Surgical Details Case Report Form (CRF).

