## 9.1.5 Secondary Efficacy Analysis

A two-sided 0.05 alpha level will be used.

For the secondary efficacy parameters when data is available, comparisons of numerical variables between subgroups (e.g. JL groups) will be made by a paired t-test or Wilcoxon rank sum test; comparisons of categorical variables between subgroups will be made by a Fisher's exact test.

One-way analysis of covariance (ANCOVA) may be used as a supportive analysis to determine if the score change from preoperative is significantly different between the subgroups after adjusting the preoperative covariates (e.g. age, gender, BMI), if appropriate.

The mean score improvement from the preoperative time point within the Triathlon® TS Outcomes Study will be summarized in tables at each nominal visit. A p-value will be presented to determine if the mean score improvement from the preoperative time point is non-zero, if appropriate.

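### Anterior knee pain and HSS Patella Score are compared between joint-line groups without regard to patellar revision, so a patellar effect may be read as a joint-line effect

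*Combined protocol and SAP*

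**What the plan says.** The second part of the plan's efficacy programme asks whether joint-line (JL) restoration affects outcome, with "specific reference to effect on postoperative stability, anterior knee pain and functional performance at 2 and 5 years postoperatively" (Section 2.1.2). Section 1.1 restricts this to a "subset of revision TKR cases with a non-replaced contralateral knee at the time of study surgery" and splits it at 5 mm. It adds that "Stability, anterior knee pain and the functional component of the KSS will be evaluated with respect to JL".

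Section 9.1.5 sets the method. For secondary parameters, "A two-sided 0.05 alpha level will be used", and "comparisons of categorical variables between subgroups will be made by a Fisher's exact test". The synopsis allows a Chi-square test as an alternative, treats anterior knee pain as categorical, and names HSS among the numerical scores compared between JL groups. The only adjustment anywhere is an ANCOVA in Section 9.1.5. It is optional and supportive, applies to score changes, and draws on preoperative covariates, with age, gender and BMI as examples.

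On the patella, Section 3.3 states: "The subject's patellar component may or may not be revised, based upon surgeon discretion". Sections 6.1 and 10.3 say the same in substance. Section 9 does not mention patellar status.

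**The concern.** The JL groups are not randomized, and neither is patellar revision. Each group can therefore contain knees with a newly revised patellar component and knees whose patella was left alone, in proportions the plan does not control. Anterior knee pain and the HSS Patella Score are the two outcomes most directly tied to the patellofemoral joint, so patellar revision could plausibly move both.

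If the proportions differ between groups, the crude test mixes the two influences. The mixing can create a difference or hide one. Hiding matters here because Section 2.1.2 expects the group above 5 mm to be non-inferior, and a masked difference would appear to confirm that. As written, the plan has no step that would show a reader whether the groups were balanced on this factor.

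**Working it through.** **Figures in the plan.** The plan states no sample size, power or event rate for the JL comparison, so there is nothing to reproduce on this point. The only sample size is for the primary KSS test: (35 × 2.486 / 7)² = 154.6 against the stated 154, and 154 / 0.85 = 181.2 against the stated 181. It has no bearing on the JL groups.

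**What the planned adjustment reaches.**
- Anterior knee pain is categorical, so the ANCOVA of score changes does not apply to it.
- HSS Patella Score change could enter the ANCOVA, but patellar revision is decided for the study operation and is not among the preoperative covariates given as examples.
- No text in Section 9 stratifies by, adjusts for or restricts on patellar status.

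**Size, under assumptions.** Suppose JL has no effect and pain depends only on patellar status. Then

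spurious difference = (difference in share revised between groups) × (difference in pain rate by patellar status).

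- Low: 0.20 × 0.10 = 0.02, or 2 points.
- High: 0.40 × 0.20 = 0.08, or 8 points.

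For the high case, with 30% revised above 5 mm, 70% revised at or below 5 mm, and pain 10% if revised and 30% if not:
- above 5 mm: 0.3 × 0.10 + 0.7 × 0.30 = 0.24
- at or below 5 mm: 0.7 × 0.10 + 0.3 × 0.30 = 0.16

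The table adds the exact probability that a two-sided Fisher test at 0.05 rejects. Every share, pain rate and group size in it is an assumption.

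| Share revised, > 5 mm / ≤ 5 mm | Pain, revised / not | Crude pain, > 5 mm / ≤ 5 mm | Difference | Odds ratio | Fisher rejects, 40 / 75 per group |
|---|---|---|---|---|---|
| 50% / 50% | 10% / 30% | 20% / 20% | 0 points | 1.00 | 2.8% / 3.1% |
| 40% / 60% | 15% / 25% | 21% / 19% | 2 points | 1.13 | 3.2% / 3.8% |
| 30% / 70% | 10% / 30% | 24% / 16% | 8 points | 1.66 | 9.6% / 17.4% |

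With balanced shares there is no bias, and Fisher's test is conservative at about 3%. At 2 points almost nothing changes. At 8 points the false-positive rate is about 10% to 17%. A still stronger imbalance (20% / 80%, pain 10% / 30%) gives 0.6 × 0.20 = 12 points and rejection of 19.6% / 37.5%. With the imbalance reversed, the same amounts would mask a true difference.

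Within each patellar stratum of these scenarios the pain rate is the same in both JL groups (for example 10% and 10%, 30% and 30%). A stratified comparison therefore has no spurious difference to detect.

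**The case against.** The strongest reply is that confounding has not been shown. It needs patellar revision to differ between the JL groups, and no text says that it does. Section 1.1 says a malpositioned joint line may lead to patellar infera, which is a consequence of JL position. It does not say that the decision to revise the patella follows JL position or the state of the patella; the protocol says only surgeon discretion. This stands. A reader might infer that patellar effects will be read as JL effects, but the documents support only that they may be.

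A second reply is that this is a secondary comparison in a non-randomized subset. That also stands, and the primary KSS conclusion is not touched. However, the objective is worded as an effect of JL restoration, and the plan has no check on an obvious co-decision made for the same operation.

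A reader might also extend the point to stability, since Section 1.1 says: "Instability can be caused by malposition of the JL, imbalance in flexion and extension gaps or incompetence of the posterior cruciate ligament", and Section 2.1.2 (Surgical Details) says: "Intraoperative gap measurements will also be obtained by using lamina spreaders to measure the tibio-femoral distance". The documents do not support adjusting for those gaps:
- They are taken once the old implant is out and before the study components are in. They describe the knee before reconstruction, not the residual imbalance that could cause instability.
- Section 2.1.2 prefers a force-reading tensor, where available, for consistency between extension and flexion. A flexion-minus-extension difference from an ordinary spreader would therefore carry unequal force rather than cancel it.
- Section 1.1 treats gap balancing as a means of achieving JL position, so adjusting for gaps could remove part of the effect under study.

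**Conclusion.** The point holds for patellar status and for two outcomes, anterior knee pain and HSS Patella Score. Section 9.1.5 compares them between JL groups with no account of a non-random surgical decision. The resulting bias is possible, not demonstrated. Its size cannot be taken from the documents: the range of 2 to 8 percentage points for pain rests wholly on assumed revision shares and pain rates, and the low end does no practical harm. No figure can be put on the HSS Patella Score.

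The point does not extend to gap mismatch and stability, and it does not affect the primary analysis. It is an inexpensive improvement to a secondary analysis.

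**What to change.** In Section 9.1.5:

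1. Tabulate patellar status at study surgery (revised or not) by JL group.
2. Beside the crude test, add an exact Cochran-Mantel-Haenszel comparison of anterior knee pain between JL groups, stratified by that status.
3. Include patellar status in the ANCOVA for HSS Patella Score change, and widen the covariate wording to allow it.
4. Describe the JL result as an association.

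No gap covariate and no logistic model for stability are needed. At most, tabulate the recorded gaps by JL group, labelled as values before reconstruction.

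The cost is SAP wording and some precision. The loss should be slight with two strata, but the subset's size is not stated, so this cannot be quantified. Patellar status should be available, because Section 10.3 applies different rules according to whether the patella was revised at study surgery. The case report forms are not in the text reviewed, so the field should be confirmed. Section 10.3 also foresees later patellar revision without study termination, so status at surgery may not be status at 2 or 5 years. Later changes should be counted by group.

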### CONFIDENTIAL

## 3.4 Estimated Study Duration

The enrollment period is estimated to be 53 months; cases will be evaluated as per the evaluation schedule until each case reaches 5 years. To allow for a learning curve with the use of the system, enrollment of cases into the study will commence when 3 cases have been completed at the center using the Triathlon TS Total Knee System.

# 4 Eligibility

The following criteria will be used to distinguish patients eligible for enrollment into this study.

## 4.1 Inclusion Criteria

- A. Patient has signed an IRB approved, study specific Informed Patient Consent Form.
- B. Patient is a male or non-pregnant female age 18 years or older at time of study device implantation.
- C. Patient is a candidate for revision of all femoral and tibial components of a total knee replacement.
- D. Patient is willing and able to comply with postoperative scheduled clinical and radiographic evaluations and rehabilitation.

## 4.2 Exclusion Criteria

- E. Patient has a Body Mass Index (BMI) > 40.
- F. Patient has an active or suspected latent infection in or about the affected knee joint at time of study device implantation.
- G. Patient has a neuromuscular or neurosensory deficiency, which limits the ability to evaluate the safety and efficacy of the device.
- H. Patient is diagnosed with a systemic disease (e.g. Lupus Erythematosus) or a metabolic disorder (e.g. Paget's Disease) leading to progressive bone deterioration.
- Patient is immunologically suppressed or receiving steroids in excess of normal physiological requirements (e.g. > 30 days).
- J. Patient has a failed unicondylar knee prosthesis.
- K. Patient has a known sensitivity to device materials.

### CONFIDENTIAL

L. Patient is a prisoner.

Exclusion Criterion F states that an infection cannot exist at the time of study surgery. It should be noted that revision for infection is not excluded. It is expected, however, that for septic failures the infection will be cleared prior to implantation of the Triathlon TS Total Knee System. For example, two-stage exchange may be performed in combination with intravenous antibiotics to clear the infection prior to implantation. Regardless of the method used, Exclusion Criterion F indicates that the infection must be cleared prior to implantation of the Triathlon TS study components.

## 5 Subject Enrollment

## 5.1 Treatment Assignment

All subjects enrolled in this study will be assigned to receive the Triathlon TS Total Knee System.

## 5.2 Randomization

This study will enroll under a non-randomized study design.

# 6 Device Description

### 6.1 Study Device

The Triathlon TS Total Knee System has been cleared for marketing in the United States, and, therefore, this study is considered a post-market assessment. All cases in this study will receive, at a minimum, the Triathlon TS Femoral Component, either the Triathlon TS Plus Tibial Insert or the Triathlon PS Tibial Insert, and the Triathlon TS Universal Tibial Baseplate.

The Triathlon TS Femoral Component and the Triathlon TS Universal Tibial Baseplate must be used in a cemented application. The subject's patellar component may or may not be revised, based upon surgeon discretion. If revised, a Triathlon Patellar Component must be used, and in a cemented application. Additionally, a variety of device accessories may be used.

### CONFIDENTIAL

### **Device Description:**

The Triathlon TS Total Knee System includes femoral components, distal and posterior femoral augments, fluted stems, cemented stems, stem extenders and offset adapters. When mated with the Triathlon TS Universal Tibial Baseplate, tibial inserts and tibial augments, the parts provide a total stabilizing knee replacement.

Figure 1 demonstrates the Triathlon TS Total Knee System excluding the Triathlon tibial augments, cemented stems, stem extenders and offset adapters. Appendix C lists all components permissible according to this study protocol.

### CONFIDENTIAL

Figure 1. Triathlon TS Total Knee System

### **FEMORAL COMPONENTS**

The Triathlon TS Femoral Component is intended for use in a cemented application. The root catalog number for the Triathlon TS Femoral Component is:

5512-F-XXX – Triathlon TS Femoral Component

#### CONFIDENTIAL

Page 19

The femoral component is available in right and left configurations, and eight proportional sizes (1 - 8) to accommodate differences in patient anatomy. The femoral component is manufactured from cobalt chrome. This component features an intercondylar box that engages the mating tibial insert eminence at approximately 40°, depending upon the size of the implant. The interior surface (except for the interior surface of the TS box) is grit-blasted to increase the surface roughness. This is intended to promote interdigitation of the polymethylmethacrylate (PMMA) bone cement with the surface texture and apposing bone. The superior portion of the box has a boss to allow for modular stem and offset attachments. There are threaded attachment features on the distal and posterior aspects of the femoral component to be used for distal and posterior augments. The threaded attachment on the distal aspect of the component also allows for the use of modular pegs.

